5.3.4.2 Assessments for pharmacokinetics and anti-therapeutic antibodies of atezolizumab

Blood samples for PK and ADA sampling in all patients in **Substudy 3** and **Cohort 4b** will be drawn in accordance with the following schedule:

- C1D1, prior to atezolizumab administration; and for PK only, 30 minutes after end of atezolizumab infusion
- C2D1, C3D1, C4D1, prior to atezolizumab administration
- C8D1, C12D1, C16D1, prior to atezolizumab administration
- 28-day Safety follow-up visit

5.3.5 Biomarker assessments

Archival (or *de novo*, if collected) tumor tissue and research liquid biopsy samples will be collected during this study to analyze a panel of biomarkers, including, but not limited to biomarkers representing MAPK (RAS/RAF/MEK/ERK), PI3K/AKT, and JAK/STAT pathways; indicating PI3K, PTEN, EGFR, MET and ERB3 signaling; demonstrating the phosphorylation status of phospho-S6, phospho-STAT, phospho-AKT, phospho-MEK, phospho-ERK.

In addition to these PD markers of target modulation, more generic markers of proliferation could be utilized to help confirm that significant inhibition of tumor proliferation has occurred. These include the proliferation index (Ki67), apoptosis levels (caspase activation), as measured by immunohistochemistry and also various measures of tumor vascularity. Anti-vascular effects may also be measured by immunohistochemistry to assess micro-vessel density and the endothelial markers CD34 and CD31.

Tumor and research liquid biopsy samples for biomarker assessments will be analyzed by the Sponsor or in specialized laboratories, as described in Section 5.3.5.2 and Section 5.3.5.1 below. Exceptions to the schedule of Biomarker assessments can be made according to the Sponsor's discretion.

5.3.5.1 Research liquid biopsy

Apart from diagnostic liquid biopsies for molecular eligibility, research liquid biopsies may comprise, but are not limited to, serum and plasma samples to analyze protein biomarkers, and cfDNA. The collection, processing, storage, and shipping of samples for the assessment of circulating biomarkers will be performed as described in the Laboratory Manual.

5.3.5.2 *Archival tumor tissue*

Archival tumor tissue should be collected from all patients enrolled with an *FGFR1–3* GA-positive test result. An FFPE block; or minimum of two H&E-stained slide plus at least 10 consecutive, unstained, 4 ± 1 μm thick sections, placed on positively charged slides, should be sent to the central laboratory for biomarker assessment, including PD-L1, as described in the Laboratory Manual.

If archival tumor tissue is not available, *de novo* biopsy may be performed but only if considered by the Investigator as safe and tolerable for the patient. For tumor tissue biopsy FFPE preservation, slide preparation and sample submission, see the Laboratory Manual.

5.3.5.3 *Pharmacodynamic research (optional)*

Patients enrolled into **Substudies 3, 4 and 5** have the option to participate in an exploratory PDR to investigate the role of CSF1R inhibition by derazantinib, comprising a skin biopsy and blood sampling for monocyte subsets prior to the first dose of study drug at the Screening visit and on C2D1. Up to 20 patients will be enrolled in this PDR Group.

The samples will be collected, processed and shipped as described in the Laboratory Manual.

5.3.5.4 *Future biomedical research*

The Sponsor will conduct Future Biomedical Research on specimens collected during this clinical study. This research may include genetic analyses (DNA), proteomics, metabolomics (serum, plasma), and/or the measurement of other analytes. Tissue/blood samples, plasma/serum samples, DNA isolates from samples available and processed during the study and not fully consumed for the described analyses may be stored and subsequently used for Future Biomedical Research.

Such research is for biomarker testing to address emergent questions not described elsewhere in the protocol as part of the main study, and will only be conducted on specimens from patients who have provided appropriate informed consent. The objective of collecting specimens for Future Biomedical Research is to explore and identify biomarkers that inform the scientific understanding of diseases and/or their therapeutic treatments. The goal is to use such information to develop safer, more effective drugs, and/or to ensure that patients receive the correct dose of the correct drug at the correct time.

The details of this Future Biomedical Research substudy are presented in [Appendix 5](#). Additional informational material for IRBs/IECs and investigational site staff is provided in [Appendix 5](#).

5.3.6 **PRO assessments**

Patient-reported outcomes will be measured using the EORTC QLQ C30, FACT-BI, EQ-5D (5L), and Health Transition Index/G-SET instruments.

The EORTC QLQ-C30 was developed to assess the quality of life of cancer patients and is the most widely used cancer-specific HR-QoL instrument. It contains 30 items and measures five functional dimensions (physical, role, emotional, cognitive, and social),

three symptom scales (fatigue, nausea/vomiting, and pain), six single symptom items (dyspnea, sleep disturbance, appetite loss, constipation, diarrhea, and financial impact) and global health and quality of life. The global health and quality of life items uses a 7-point scale scoring with anchors (1=very poor and 7=excellent); the other items are scored on a 4-point scale (1=not at all, 2=a little, 3= quite a bit, 4=very much).

The EORTC QLQ-C30 is the most frequently utilized and reported patient reported outcome measures in cancer clinical trials. The reliability, validity and practicality of these instruments have been reported ([Aaronson 1993](#)).

The FACT-BI is instrument which was developed for patients with bladder cancer. It contains 40 items and consists of the five subscales: physical well-being (PWB), functional well-being (FWB), emotional well-being (EWB), social well-being (SWB) and an additional scale specific to bladder cancer. In addition, the PWB, FWB, EWB, and SWB subscales can be summed to form the FACTGeneral (FACT-G) score and the FACT-BL total score (FACT-G and the bladder cancer specific scale). The items are scored on a 4-point scale (0=not at all, 1=a little bit, 2= somewhat, 3=quite a bit, 4 = very much) ([Karvinen 2007](#)).

The EQ-5D (5L) is a standardized instrument for use as a measure of health outcome. The EQ-5D will provide data for use in economic models and analyses including developing health utilities or QALYs. The five health state dimensions in this instrument include the following: mobility, self-care, usual activities, pain/discomfort, and anxiety/depression. Each dimension is rated on a five-point scale from 1 (no problem) to 5 (extreme problem). The EQ-5D also includes a graded (0 to 100) vertical VAS on which the patient rates his or her general state of health at the time of the assessment.

The Health Transition Index/G-SET is a single item and will be used as an external anchor to determine the minimal important difference of the EQ-5D visual analogue scale, EORTC QLQ-C30 scales and FACT-BI scales. It will be administered twice during the study following the recent protocol by the EORTC Quality of Life Group ([Musoro 2018](#)) for evaluating the minimal important difference. The SET will be provided after 6 weeks (at C3D1) and 12 weeks (at C5D1). The SET is a patient-rated change in health between two time periods using a five point ordinal scale (1=much better now than six weeks ago; 2=somewhat better now than six weeks ago; 3=about the same as six weeks ago; 4=somewhat worse now than six weeks ago; 5=much worse now than six weeks ago, the recall period was adapted compared to the original item) ([Ware 2002](#), [Lloyd 2014](#)).

The HR-QoL questionnaires will be provided to the patients to complete prior to being evaluated by the physician on D1 of every cycle, and at the End of Treatment visit.

Either a paper instrument or an electronic PRO data collection method may be used. The PRO instruments, translated as necessary into the local language, will be distributed by the Investigator's staff and completed by the patient. To ensure instrument validity, and to ensure that data standards meet Health Authority requirements, PRO instruments should be self-administered at the investigational site before the patient sees the physician (i.e., at the start of the visit) and prior to the completion of other study assessments and the

administration of study treatment. The questionnaire should be completed by the patient without assistance during their scheduled visit(s) at the clinic. Study site staff should review all instruments for completeness before the patient leaves the investigational site. The EQ-5D will always be completed by patients before completing the EORTC QLQ-C30, FACT-BI, and the Health Transition Index/G-SET (only at visits after 6 and 12 weeks).

6 STUDY TREATMENTS

Derazantinib and atezolizumab are both considered to be IMPs in this study, and will be provided by the Sponsor. Detailed information related to IMP handling and storage is provided in the Pharmacy Manual.

As this is an open-label study, neither the patient, the Investigator / site staff, nor the Sponsor will be blinded to the treatment administered.

6.1 Investigational products

6.1.1 Derazantinib

Derazantinib is an investigational drug supplied as 100 mg powder-filled capsules for oral administration.

The Investigator must ensure that derazantinib capsules will be used only in accordance with the protocol.

6.1.1.1 *Derazantinib administration*

Derazantinib capsules will be administered by mouth. The schedules for the administration of derazantinib are shown in Section 6.1.3 and Table 6.

Derazantinib capsules should be administered at least 1 hour before, or at least 2 hours after, a meal. In the event of nausea or vomiting which is assessed as CTCAE grade ≥ 2 , a light meal before subsequent derazantinib administration is allowed, to minimize the severity of the event.

6.1.1.2 *Labeling and packaging*

Derazantinib is supplied as capsules in white/opaque high-density polyethylene bottles with white/opaque polypropylene caps and labeled in the local languages as investigational agent, in accordance with local regulations and the Annex 13 Good Manufacturing Practice rules.

Labels must include the identity of the Sponsor and Investigator, patient number, protocol number, drug identification, storage conditions, content of study drug, and expiry date. Information on drug shipment including temperature logger and acknowledgement of receipt form to be completed by the receiver must also be included in the shipment.

6.1.1.3 *Drug accountability*

When a drug shipment is received, the Investigator or designee will check the amount and condition of the drug, check for appropriate local language in the label, drug expiration date, and acknowledge receipt in the IWRS system. A Packing Slip will be included with the shipment and must be completed upon receipt and returned as instructed on the form. In addition, the Investigator or designee shall contact the Sponsor as soon as possible if there is a problem with the shipment.

A Drug Accountability Log will be provided for derazantinib capsules. The log must be kept current and should contain the protocol number, the name and clinical site of the

Investigator, dates and quantities of drug received, patient's identification number to whom derazantinib capsules were dispensed, the date and quantity dispensed, and balance remaining, if from individual patient drug units, as well as the lot number, dose, and the initials of the dispenser. Drug accountability is performed to the capsule level.

To avoid unnecessary waste of derazantinib capsules, in cases where treatment was interrupted and/or dose was reduced, the patient can continue dosing from the previously dispensed bottle until the next drug dispensing visit where re-supply is needed to maintain the protocol dosing regimen.

At the end of the study or as directed, all study drugs, including unused, partially used, or empty containers, will be returned to the designee as instructed by the Sponsor. Derazantinib capsules will be returned only after the study monitor has completed a final inventory to verify the quantity to be returned. The return of derazantinib capsules must be documented and the documentation must be included in the shipment. Unused drug supplies may be destroyed by the Investigator when approved in writing by the Sponsor and the Sponsor has received copies of the site's drug handling and disposition Standard Operation Procedures (SOPs) or equivalent.

All derazantinib capsules inventory forms must be made available for inspection by a Sponsor authorized representative or designee and regulatory agency inspectors. The Investigator is responsible for the accountability of all used and unused study supplies at the site.

6.1.1.4 Shipping and storage conditions

The Sponsor will provide derazantinib capsules required for completion of this study. It will be shipped to the pharmacist/study personnel at the clinical sites during the study with orders being raised via the IWRS.

Drug supplies must be stored in a secure, limited access storage area.

The packaged drug product should be shipped and stored at controlled room temperature 20°C–25°C (68°F–77°F); allowable excursions are in the range of 15°C–30°C (59°F–86°F). Derazantinib capsules are stable when stored at controlled room temperature. Refer to the product label for specific storage conditions and handling requirements.

If storage conditions deviate from the above storage requirements, the Investigator will document the deviation and inform the study monitor within 24 hours of discovery of the deviation. The supplies should be held in quarantine and not dispensed until the deviation has been reviewed by the Sponsor's Quality Assurance or designee. If it is determined that the product is no longer suitable for use, the bottles must be reported as damaged in the IWRS and a resupply shipment will be made.

6.1.1.5 Dose modifications

In general, once the dose of derazantinib has been modified for a patient (as per [Table 4](#)), all subsequent cycles should be administered to that patient at the modified dose. The modified dose will be considered the maximum dose for all subsequent cycles for that patient.

When a drug-related toxicity is observed, dose delays and/or reductions in derazantinib administration are allowed. A drug-related toxicity is defined as any toxicity considered probably, or possibly related to derazantinib. If dose reduction is indicated, a patient should be assigned to the lower dose. Dose re-escalation is not permitted. In the event of a dose modification, the dose change(s) must be captured in the eCRF. If questions or considerations regarding dose modification arise or a specific dose modification is needed, the Sponsor's Medical Monitor or designee should be consulted.

Table 4 Derazantinib dose reduction schema

Current dose	Dose after reduction
2 capsules BID (400 mg daily)	3 capsules QD (300 mg daily)
3 capsules QD (300 mg daily)	2 capsules QD (200 mg daily)
2 capsules QD (200 mg daily)	1 capsule QD (100 mg daily)
1 capsule QD (100 mg daily)	1 capsule QOD (100 mg every other day)

Abbreviations: BID, twice a day; QD, once daily; QOD, every other day

For AEs of special interest (AESIs; see Section 7.2.6), including hyperphosphatemia and eye disorders, and any other AEs considered at least possibly derazantinib-related (see Section 7.1.1.2 for risks for derazantinib), Table 5 and Sections 6.1.1.5.1 to 6.1.1.5.3 provide specific guidance to manage these events through dose delays, reductions and/or discontinuations.

Table 5 Dose delays/reductions for drug-related toxicity

Hyperphosphatemia	
Serum phosphate level	Action
	(For serum phosphate ≥ 7.0 mg/dL, consider adding an oral phosphate binding/reducing agent until serum phosphate level returns to < 5.6 mg/dL)
< 7.0 mg/dL (< 2.26 mmol/L)	Continue derazantinib at current dose.
7.0 – 9.0 mg/dL (2.26 – 2.90 mmol/L)	Withhold derazantinib with weekly reassessments until the level returns to < 5.6 mg/dL; the patient may restart derazantinib at the dose prior to hyperphosphatemia. If hyperphosphatemia lasts > 2 weeks, consider restarting at the next lower dose.
> 9.0 – 10.0 mg/dL (> 2.90 – 3.23 mmol/L)	Withhold derazantinib with weekly reassessments until the level returns to < 5.6 mg/dL; the patient may restart at the next lower dose level.
> 10.0 mg/dL (> 3.23 mmol/L) or significant alteration from baseline renal function or Grade 3 hypercalcemia	Withhold derazantinib with weekly reassessments until the level returns to < 5.6 mg/dL; the patient may restart at two dose levels lower, or permanently discontinue derazantinib (e.g., if considered life threatening event).
Central serious retinopathy / Retinal pigment epithelial detachment	
Grade	Action
Asymptomatic clinical or diagnostic observations only (Grade 1)	Withhold derazantinib until resolution. If the event resolves within 4 weeks, restart at the next lower dose level. If stable but not resolved for two consecutive eye examinations, restart at the next lower dose level.
Visual acuity 20/40 or better or ≤ 3 lines of decreased vision from baseline (Grade 2)	Withhold derazantinib until resolution. If the event resolves within 4 weeks, the patient may restart at the next lower dose level.
Visual acuity worse than 20/40 or > 3 lines of decreased vision from baseline (Grade 3)	Withhold derazantinib until resolution. If the event resolves within 4 weeks, the patient may restart at two dose levels lower. If the event recurs, consider permanent discontinuation of derazantinib.
Visual acuity 20/200 or worse in affected eye (Grade 4)	Permanently discontinue derazantinib.
Other events	
CTCAE grade	Action
Grade 1 or 2	Continue derazantinib at current dose, unless dose delay/modification may be clinically indicated (as assessed by the Investigator and agreed upon by the Medical Monitor or designee).
Grade 3	Withhold derazantinib until recovery to Grade 1 or baseline; administer derazantinib at the next lower dose for subsequent dosing, unless further dose reduction is required.
Grade 4	Permanently discontinue derazantinib if the event is at least possibly related to derazantinib.

Abbreviations: CTCAE, Common Terminology Criteria for Adverse Events.

6.1.1.5.1 *Hyperphosphatemia*

For all patients, it is recommended to restrict phosphate intake to 600–800 mg daily. As hyperphosphatemia is only defined by NCI CTCAE 5.0 with regards to escalating interventional measures (without specifications triggering these interventions) and not by laboratory values exceeding the upper limits of normal leading to specific interventions, [Table 5](#) guides interventions for the management of hyperphosphatemia considered at least possibly related to derazantinib.

In alignment with interventions to ensure patient safety and for the purpose of this protocol, hyperphosphatemia is defined as:

- Grade 1: > ULN to < 7.0 mg/dL (< 2.26 mmol/L)
- Grade 2: Non-invasive intervention required (e.g., withhold drug or modify dose) or between 7.0 – 9.0 mg/dL (2.26 – 2.90 mmol/L)
- Grade 3: Severe or medically significant, but not immediately life threatening or > 9.0 – 10.0 mg/dL (> 2.90 – 3.23 mmol/L)
- Grade 4: Life-threatening consequences, urgent intervention indicated e.g., dialysis or > 10.0 mg/dL (> 3.23 mmol/L)

Patients who present with serum phosphate ≥ 7.0 mg/dL, adding an oral phosphate binding/reducing agent¹ until serum phosphate level returns to < 5.6 mg/dL should be considered, and patients should be instructed to adhere to a low-phosphate diet.

6.1.1.5.2 *Management of retinal adverse events*

A complete ophthalmological examination (see Section 5.3.2.3) should be performed by an ophthalmologist at the Screening visit, for the first four cycles (i.e., Day 1 of Cycles 2–5), and at the End of Treatment visit. Further complete ophthalmological examinations only need to be performed if clinically indicated. [Table 5](#) provides specific guidance for the management of dose delays/reductions in the case of retinal adverse events possibly related to derazantinib.

6.1.1.5.3 *Management of QTc prolongation or other significant ECG abnormalities*

If significant QTc prolongation and/or significant ventricular arrhythmia is observed, i.e., a prolonged QTcF interval ≥ 501 ms on at least two separate ECGs (mean values from triplicate ECGs, consistent with a CTCAE grade 3 event), the patient must be monitored by the Investigator and hourly (triplicate) 12-lead ECG obtained until the mean QTcF has returned to ≤ 450 msec for males or to ≤ 460 msec for females. The clinical context and possible factors contributing to QTc prolongations such as electrolyte abnormalities (potassium, calcium or magnesium), concomitant medications, or other clinical factors such as cardiac ischemia must be carefully assessed, and any findings documented in the eCRF. The decision to continue treatment with derazantinib should be reviewed and supported by a cardiologist.

¹ Either calcium-containing (e.g., calcium carbonate and calcium acetate) or non-calcium-containing (e.g., sevelamer) phosphate binders, and/or phosphaturic agents, depending on serum calcium levels and in accordance with institutional guidelines, recommendations, and schedules.

Once QTc prolongation has resolved, and if a decision was made to continue treatment with derazantinib, patients may continue treatment at a lower dose with an ECG monitoring schedule defined by the cardiologist. Patients who experience a mean QTcF interval ≥ 501 ms on at least two ECGs at different timepoints after dose reduction will be discontinued from study.

All significant QTc prolongations or other relevant ECG abnormalities, will also be evaluated centrally.

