3.1.7 Survival Follow-up period

Patients who are permanently discontinued from study treatment for reasons other than death and consent withdrawal for further safety and survival follow-up, regardless of the reason, will enter the survival follow-up period (see Section 5.2.3).

Survival Follow-up (at least every 3 months \pm 14 days from last dose of study drug) will start on the day of the last dose of either study drug and will continue until the study has completed (see Section 3.1.8) or other discontinuation criteria are met (see Section 4.4.4).

All subsequent anticancer therapies should continue to be recorded on the appropriate electronic case report form (eCRF) for the duration of the patient's survival follow up.

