4.4 Method of assignment to substudy and treatment

Patients will be assigned to a specific substudy based on the appropriate eligibility criteria.

For all substudies, a unique enrollment code will be assigned after written informed consent has been obtained, using the centralized Interactive Web Response System (IWRS). If a patient withdraws from participation in the study, his or her enrollment code will not be reused.

4.4.1 Substudy 1

All eligible patients will receive derazantinib 300 mg QD monotherapy. Treatment assignment is performed on C1D1, or as close as possible to the date on which treatment is to be administered.

4.4.2 Substudy 3

All eligible patients will receive derazantinib 200 mg BID and atezolizumab 1200 mg Q3W in combination. If derazantinib 200 mg BID at the safety interim analysis is not assessed as safe and tolerable, patients will be treated with the RP2D determined in Substudy 2 (i.e., derazantinib 300 mg QD and atezolizumab 1200 mg Q3W in combination). Treatment assignment is done on C1D1, or as close as possible to the date on which treatment is to be administered.

4.4.3 Substudy 4

Patients in **Substudy 4** are to be randomized (1:1) to receive study treatment with either derazantinib 300 mg QD monotherapy (**Cohort 4a**), or derazantinib 300 mg QD and atezolizumab 1200 mg Q3W in combination (**Cohort 4b**), based on a computer-generated randomization schedule via IWRS. Patients in Substudy 4 will be randomized on C1D1, or as close as possible to the date on which treatment is allocated. Randomization will be stratified for key prognostic factors according to the following algorithms:

- The presence of visceral metastasis, an ECOG PS of 2, or a preceding FGFR inhibitor treatment interval of less than 6 months (i.e., less than 24 full weeks) will be credited with one point, and patients will be stratified according to their composite score values of 0–1 versus 2–3 points.

4.4.4 Substudy 5

All eligible patients will receive derazantinib 200 mg BID monotherapy. Treatment assignment is performed on C1D1, or as close as possible to the date on which treatment is to be administered.

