4.5 Discontinuation from the study treatment or study

4.5.1 Patient discontinuation from study treatment

Patients should be discontinued from study treatment at any time if they experience documented radiographic progression of disease. Patients will be permitted to remain on study treatment after RECIST 1.1 criteria for PD are met **only** if, in the opinion of the Investigator and with the agreement of the Medical Monitor, they continue to derive benefit from derazantinib or derazantinib-atezolizumab in combination.

In particular, for patients in **Cohort 4a**, every effort should be undertaken to obtain BICR confirmation on disease progression, in order to establish a baseline for a potential crossover.

Furthermore, patients should be discontinued from study treatment should any of the following occur:

- Any clinically unacceptable treatment-emergent toxicity occurring in patients treated with derazantinib monotherapy that persist despite optimal treatment or dose reduction
- Any clinically unacceptable treatment-emergent toxicity clearly attributable to derazantinib occurring in patients treated with derazantinib-atezolizumab in combination that persist despite optimal treatment or derazantinib dose reduction. In this instance derazantinib should be discontinued, whilst continuation of atezolizumab is at the discretion of the Investigator
- Any clinically unacceptable treatment-emergent toxicity clearly attributable to atezolizumab occurring in patients treated with derazantinib and atezolizumab in combination that require respective management, as detailed in [Appendix 4](#)
- Both study drugs (derazantinib and atezolizumab) should be discontinued for instances of overlapping toxicity (e.g., ophthalmological and/or hepatic adverse events) that cannot be clearly attributed to either drug
- Pregnancy (see Section [7.4.5](#))
- Patient decision to discontinue treatment and study visits
- Withdrawal of consent from treatment and study follow up calls
- Non-compliance with any part of the study, as assessed by the Investigator or Medical Monitor
- Investigator's decision after discussion with the Medical Monitor or designee
- Death

For all patients who discontinue derazantinib, AE monitoring must be continued for at least 28 days after the last dose of study drug (see Section 5.2.2.8); for patients discontinuing atezolizumab, AE monitoring must be continued for at least 90 days after the last dose (see Section 5.2.2.9).

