4.5.2 Patient discontinuation from the study

Patients who discontinue from study treatment will be followed for survival until the end of the study criteria are met (see Section 3.1.8), either through direct contact with the patient or the patient's relatives, or collection of public records (e.g., death certificate) in accordance with local laws, unless they meet any of the following criteria:

- Withdrawal of consent for study treatment including safety and survival follow up
- Withdrawal of consent for long-term (survival) follow-up
- Lost to follow-up
- Death

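### The repeat-QTc rule in Protocol 6.1.1.5.3 takes patients out of the study, where the rest of the protocol would only stop treatment (internal inconsistency, minor)

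*Protocol*

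**What the plan says.** Section 6.1.1.5.3 sits among the derazantinib dose-modification rules. After a first episode of significant QTc prolongation, a cardiologist must support any decision to continue derazantinib, and dosing may then resume at a lower dose. If mean QTcF reaches 501 ms or more again, on two or more ECGs, patients who meet the criterion "at different timepoints after dose reduction will be discontinued from study".

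The sections that govern discontinuation say something else:

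- **4.5.1 (stopping treatment).** Unacceptable toxicity that persists despite dose reduction is a reason to stop study treatment. For combination patients whose toxicity is clearly due to derazantinib: "In this instance derazantinib should be discontinued, whilst continuation of atezolizumab is at the discretion of the Investigator". Both drugs "should be discontinued for instances of overlapping toxicity (e.g., ophthalmological and/or hepatic adverse events) that cannot be clearly attributed to either drug". On safety follow-up: "For all patients who discontinue derazantinib, AE monitoring must be continued for at least 28 days after the last dose of study drug". For atezolizumab the minimum is 90 days.
- **4.5.2 (leaving the study).** "Patients who discontinue from study treatment will be followed for survival until the end of the study criteria are met", unless one of four listed exits applies: two forms of consent withdrawal, loss to follow-up, or death.
- **3.1.7 (survival follow-up).** Patients who permanently stop treatment, other than through death or withdrawal of consent to follow-up, "regardless of the reason, will enter the survival follow-up period".

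SAP 6.3.2.4 censors overall survival at last study contact when no date of death is recorded.

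**The concern.** Taken at its word, the QTc sentence creates a toxicity-driven exit from the study that 4.5.2 does not list and 3.1.7 rules out. Two things would be at stake if a site acted on it.

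The first is safety. The 28-day visit (5.2.2.8) includes a triplicate ECG and follow-up of unresolved drug-related events, and QT prolongation is an event of special interest (7.2.6). A patient with recurrent QTcF of at least 501 ms is one for whom that visit matters most.

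The second is overall survival. If survival contact stopped, the patient would be censored at last contact because of a toxicity. Censoring for that reason may be related to prognosis, whereas the Kaplan-Meier estimate assumes that it is not.

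**Working it through.** This is a question of consistent wording, and the plan states no figure to reproduce. The relevant provisions compare as follows.

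| Protocol section | What it ends | Does toxicity end follow-up? |
|---|---|---|
| 6.1.1.5.3, final action on repeat QTc | Study participation | Yes, if read literally |
| 6.1.1.5.3, preceding sentences | Concern continuing derazantinib | No |
| Table 5, other severe toxicities | Derazantinib | No |
| 4.5.1 | Study treatment, by drug | No; monitoring for at least 28 or 90 days |
| 4.5.2 | Study participation | No; four exits, none for toxicity |
| 3.1.7 and 5.2.3.1 | Neither; set up survival contact | No |

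**Is it a slip?** The subsection deals with derazantinib dosing, its preceding sentences concern continuing derazantinib, and Table 5 uses derazantinib as the object of discontinuation. Section 6.2.1 refers to study treatment when it means treatment. The intended object was therefore probably derazantinib or study treatment. The text does not settle which.

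**Does any clause support a study exit?** Survival follow-up may also end under 3.1.7 when the study completes "or other discontinuation criteria are met (see Section 4.4.4"). The section cited there is the Substudy 5 treatment assignment, which opens: "All eligible patients will receive derazantinib 200 mg BID monotherapy". It contains no discontinuation criteria, so the clause neither supports the QTc sentence nor tells a site how to read it. Section 5.2.3.1 repeats the wrong reference, and 3.1.5 gives it twice.

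**Combination patients.** If the QTc event is clearly attributable to derazantinib, 4.5.1 leaves atezolizumab to the Investigator, and a literal study exit removes that choice. If attribution is unclear, 4.5.1 already stops both drugs and there is no conflict over atezolizumab.

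**Which analyses could change if survival contact stopped?**

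- Overall survival: yes, through censoring at last contact (SAP 6.3.2.4).
- PFS sensitivity analysis 2 (SAP 6.3.2.3): deaths after treatment could be missed. Survival contact records vital status and later therapy, not scans, so it supplies no radiographic progressions. Censoring at new anti-cancer treatment may come first in any case.
- Main PFS: no. Patients who stop treatment without progression are already censored at their last scan before end of treatment.
- Objective response rate: no. Best overall response is taken up to End of Treatment (Protocol Appendix 2).

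**Drug remaining at the 28-day visit.** Section 1.4.3.1 gives a half-life of 8 to 10 days. Assuming simple first-order decay after the last dose, the fraction left at day 28 is 0.5^(28/8) = 0.5^3.5 ≈ 0.09 for 8 days, and 0.5^(28/10) = 0.5^2.8 ≈ 0.14 for 10 days. About 9% to 14% remains, which supports keeping the 28-day ECG.

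**How many patients?** This cannot be derived. The trigger needs a sequence: significant prolongation on at least two ECGs, resolution, a cardiologist-supported decision to continue at a lower dose, and recurrence on at least two ECGs. The QT footnote to Section 1.5.1 classes QT prolongation as a non-important potential risk and says the central ECG data exclude a mean QTcF effect above 20 ms.

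**The case against.** The best defence is that the protocol already answers the question. Sections 4.5.1, 4.5.2, 3.1.7 and 5.2.3.1 all require follow-up to continue, and Table 1 schedules survival contact for all substudies. Against them stands one loosely used word in a dosing subsection that does not mention follow-up. Similar looseness occurs elsewhere: 3.1.6.2 describes Cohort 4a patients as withdrawing from the main study although they go on to crossover treatment, and 9.1.2 speaks of withdrawal from the study because of an adverse event. Data are lost only if a site lets this sentence override the others.

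Most of this stands, and it is why the point is minor. It does not remove the contradiction. The sentence is an operative safety instruction, and a site handling a recurrent QTc event would consult it directly.

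A reader might go further and infer that the wording damages the response rate or main PFS, because a combination patient could lose atezolizumab early. The documents do not support that. It would need a combination patient, the full QTc sequence, clear attribution to derazantinib, an Investigator who wished to continue atezolizumab but felt barred, and a response first reached or confirmed later on atezolizumab alone. The documents give no figure for any of these steps, and 4.5.1 makes continued atezolizumab discretionary in any case.

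**Conclusion.** The sentence is wrong as written. It conflicts with 4.5.1, 4.5.2 and 3.1.7, and is probably a slip for derazantinib or study treatment. That reading is an inference from the surrounding text.

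The consequence is conditional. If a site followed the sentence literally, safety follow-up and survival contact could end for a toxicity reason, and overall survival would be censored at last contact. Few or no patients are likely to be affected, and overall survival is secondary. No effect on the objective response rate, the two-stage decision rules or main PFS is claimed.

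A reader might also take the sentence as a deliberate additional study exit. The list in 4.5.2 does not include it, and the clause in 3.1.7 that might have allowed it cites a section with no such criteria.

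Severity is minor. This is an internal inconsistency, not a disputed design choice.

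**What to change.** In 6.1.1.5.3, replace the final action with: *will permanently discontinue derazantinib (atezolizumab per Section 4.5.1); safety follow-up (28 days, and 90 days if atezolizumab was received) and survival follow-up continue.* Referring to 4.5.1 keeps its attribution rules for combination patients.

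As a separate clerical correction, redirect the four references to 4.4.4: the two in 3.1.5 to 4.5.1 and 4.5.2 as applicable, and those in 3.1.7 and 5.2.3.1 to 4.5.2.

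The cost is one phrase and four cross-references. No visits are added beyond those in Table 1, and the SAP needs no change.
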